days, and mice irradiated with BMX-001 had an average survival of 63 days. Thus, BMX-001 did not protect head and neck tumor cells from radiation sensitization; in fact, BMX-001 further sensitized the head and neck tumor to irradiation and enhanced the survival of tumor bearing animals. This demonstrates that BMX-001 has differential effects in tumor tissue compared to normal tissues, with BMX-001 showing potential to protect normal tissues and sensitize tumors to RT. Thus, the rationale for this protocol is based on the demonstrated dual activity of BMX-001 to protect normal tissue while sensitizing tumors to therapy [19].

Preclinical safety toxicology studies have shown a No Observable Effect Level (NOEL) in mice of 12 mg/kg and in cynomolgus monkeys of 2 mg/kg. BioMimetix has concluded a Phase 1 dose escalation study in newly diagnosed high-grade glioma patients. This clinical trial has demonstrated no adverse effects in subcutaneous dosing up to 28 mg/subject load with half the loading dose given biweekly for 8 weeks in 12 subjects. Three subjects were enrolled and dosed with 42 mg/subject load with half the loading dose given biweekly for 8 weeks. Of these three subjects, there was one dose-limiting toxicity of grade 3 tachycardia and grade 3 hypotension. The DLT in this subject occurred with the loading dose (42 mg sc). The patient was treated with fluids and hospital admitted for observation for 24 hours during which time the hypotension and tachycardia resolved. The cardiac rhythm was a sinus tachycardia and no other cardiac toxicity was observed. The tachycardia was assumed to have resulted from hypotension occurring following the sub-cutaneous injection of BMX-001 (42 mg). After the loading dose of BMX-001 and the described DLT, the subject continued on study and experienced no tachycardia or hypotension following administration of the subsequent 16 maintenance doses (20 mg sc).

The most common related toxicity see in this Phase 1 trial was injection site reaction and all of these have been grade 1. There is no apparent toxicity to end organ tissues or bone marrow.

The completion of a Phase 1 clinical trial in patients with high-grade glioma undergoing brain radiation therapy plus chemotherapy with temozolomide has established an MTD for BMX-001. The MTD by sub-cutaneous injection is 28 mg/subject load followed by a maintenance dose of 14 mg/subject b.i.w. At the MTD, there have been no BMX-001 dose limiting toxicities observed.

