Based on the completion of Phase 1 and establishment of an MTD for this treatment regimen in patients undergoing radiation therapy and chemotherapy, this clinical trial of head and neck cancer patients will proceed to a Phase 2 trial of 48 subjects with a safety lead-in of 6 subjects. The reason for the safety lead-in is to confirm safety in subjects receiving radiation therapy to the head and neck area and with chemotherapy involving cisplatin.

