We will do a safety lead-in trial for head and neck cancer patients involving 6 subjects at the 28 mg/subject loading dose given by subcutaneous injection followed by one-half the loading dose (14mg/subject) administered by subcutaneous injection biweekly during the remainder of the trial. We will assess safety in a lead-in cohort of 6 head and neck cancer patients being treated with cisplatin and radiation therapy. Once those 6 subjects are enrolled, we will then move to full Phase 2 open enrollment. Based on the preclinical safety toxicology studies in mice and monkey and the results of the Phase 1 BMX-001 high-grade glioma trial in humans, we anticipate that a dose of 28 mg/subject load followed by one-half the loading dose (14 mgs) twice weekly will not have dose-limiting toxicities in patients enrolled in this study. If this expectation is confirmed (meaning there are no definite BMX-001-related dose-limiting toxicities, defined as grade 3 study-drug-related adverse events), this dose will be utilized in the full Phase 2 trial enrolling an additional 42 subjects. If one or more definite BMX-001 related grade 4 or 5 DLTs occur in the 6 patient safety lead-in cohort, accrual will pause pending review by the sponsor and DSMB. Non

BMX-001 related DLTs are anticipated in this patient population due to the primary disease and treatment regimen.

This is not a randomized trial. All eligible patients enrolled will receive BMX-001.

A maximum of 48 patients will be enrolled in this Phase 2 clinical trial.

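### Section 4.3.2: a definite grade 3 DLT in the safety lead-in fails the condition for carrying the dose forward, but no pause or dose decision follows

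*Combined protocol and SAP*

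**What the plan says.** Section 4.3.2 puts six subjects on the 28 mg load and 14 mg maintenance dose before the main Phase 2 cohort. Section 4.2 gives the purpose: "The reason for the safety lead-in is to confirm safety in subjects receiving radiation therapy to the head and neck area", together with cisplatin.

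Section 4.3.2 then makes three statements:

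- Opening of enrolment: "Once those 6 subjects are enrolled, we will then move to full Phase 2 open enrollment".
- Go condition: the sponsor expects no dose-limiting toxicity. If that is borne out ("meaning there are no definite BMX-001-related dose-limiting toxicities, defined as grade 3 study-drug-related adverse events"), then "this dose will be utilized in the full Phase 2 trial enrolling an additional 42 subjects".
- Pause trigger: "If one or more definite BMX-001 related grade 4 or 5 DLTs occur in the 6 patient safety lead-in cohort, accrual will pause", until the sponsor and DSMB have reviewed.

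Section 11.11 defines a DLT more broadly. It counts events possibly, probably or definitely attributable to BMX-001, from the first dose to 4 weeks after chemoradiation (CRT) ends. Non-haematologic events generally count from grade 3, with a few exclusions. Some entries carry no grade, such as a re-treatment delay of more than 14 days for unresolved haematologic toxicity, or failure to complete 75% of the planned radiation dose.

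**The concern.** The go condition and the pause trigger sit in adjacent sentences and use different grades. A definite grade 3 DLT means the dose has not been confirmed by the plan's own test, but the plan does not say what happens next to accrual or to the dose.

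This is the part of the rule most likely to be tested. The glioma Phase 1 trial reported a single DLT, at the 42 mg load: "Of these three subjects, there was one dose-limiting toxicity of grade 3 tachycardia and grade 3 hypotension". Phase 1 of the present trial stopped at a 14 mg load, so the lead-in is the planned safety check of 28 mg with cisplatin and head-and-neck radiation. If the same grade of event occurred here and was judged definite, investigators, sponsor and DSMB would have no agreed rule while new subjects were starting the same dose.

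**Working it through.** The plan gives no operating characteristic for the lead-in, so there is no figure to reproduce. The check has three parts.

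**1. Set the two rules against each possible lead-in result (definite attribution).**

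| Worst definite event in the six | Go condition (4.3.2) | Pause trigger (4.3.2) | Cohort-level action |
|---|---|---|---|
| No DLT | met | not met | dose goes forward |
| Grade 3 DLT | fails | not met | **none stated** |
| Grade 4 or 5 DLT | fails, if grade 3 is read as a minimum | met | pause and review |
| DLT with no grade (11.11) | unclear, because of the grade 3 description | not met | **none stated** |

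The gap in the second row does not depend on how the grade 3 description is read. Taken as exactly grade 3 or as grade 3 and above, the go condition fails and the trigger is silent.

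**2. Look for another section that fills the gap.**

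- 11.6 repeats that there is a lead-in and adds no rule.
- 11.9 discontinues BMX-001 for attributable events of grade 3 or above, and 13.2 bars re-treatment during a DLT. Both act on the individual patient.
- 14.3 requires the sponsor to notify the DSMB within 48 hours of a grade 3-5 DLT that is probably or definitely related, and allows ad hoc meetings. It requires no pause and no dose decision.
- 13.6.1 lets the investigator or sponsor end the study at any time. This is discretionary.

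None of these assigns a cohort-level action to a definite grade 3 DLT.

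**3. See whether accrual is running when such an event could appear.** Inputs: loading dose on day -4 to 0 (Section 13 schedule), so 0 to 4 days before CRT; CRT for 6-7 weeks (13.1.1); radiation allowed into week 8 (footnote to the Section 13 schedule); DLT period to 4 weeks after CRT (11.11).

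Window in weeks = (0 to 4 days)/7 + CRT weeks + 4.

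- 6 weeks of CRT: 0 + 6 + 4 = 10.0, to 4/7 + 6 + 4 = 10.6.
- 7 weeks: 0 + 7 + 4 = 11.0, to 4/7 + 7 + 4 = 11.6.
- Radiation to the end of week 8: 0 + 8 + 4 = 12.0, to 4/7 + 8 + 4 = 12.6.

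Full enrolment opens when the sixth subject enrols, before that subject's window has run. For about 10 to 12.6 weeks from that subject's loading dose, the go condition cannot be fully assessed while accrual is open.

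**The case against.** The strongest reply is that the scheme is deliberately tiered: grade 3 brings DSMB notice and a patient-level stop, and grade 4 or 5 brings an automatic pause. That is a defensible policy, and the 48-hour notice is a real safeguard. But if it is the policy, the go condition contradicts it, because it makes a definite grade 3 DLT enough to leave the dose unconfirmed. One of the two sentences still has to change.

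A second reply is that the risk is low. In glioma, "At the MTD, there have been no BMX-001 dose limiting toxicities observed". The grade 3 event came at 42 mg, 1.5 times the present load (42/28), and afterwards "the subject continued on study and experienced no tachycardia or hypotension following administration of the subsequent 16 maintenance doses". This stands as mitigation. It does not supply the missing rule, and the lead-in exists because radiation site and chemotherapy differ here.

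A reader might go further in two ways that the documents do not support:

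- One might infer that the plan permits the dose to go forward after a definite grade 3 DLT. It does not. Use of the dose is conditional and the condition has failed; what is missing is the consequence.
- One might infer that opening enrolment before the sixth subject clears the DLT period is itself an error. It is a readable design choice. The present trigger has no end date and already covers later events in those six subjects. Timing matters only because it means the default, absent a decision, is continued accrual.

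Finally, the lead-in may be over. Section 11.10.4 places a BMX-HN-001 subject, apparently from this trial, among those given a 28 mg load by April 2019. The documents do not say whether the lead-in decision has been taken.

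**Conclusion.** The concern holds as a mismatch between two rules in Section 4.3.2. A definite grade 3 DLT among the six lead-in subjects fails the go condition, and no section requires a pause or a decision on the dose. The conclusion rests on the current text alone and needs no assumed rate.

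Its size is one unassigned outcome in the lead-in decision, with accrual open during a window of about 10 to 12.6 weeks for the sixth subject. The upper end assumes that radiation runs to the end of week 8 and that loading is 4 days before CRT.

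A reader might want a probability of landing in the gap, or a count of subjects exposed. The documents do not support either. They give no rate of definite grade 3 DLTs at 28 mg in this population, and the only accrual pace is a maximum of 54 subjects over 48 months that includes the completed Phase 1.

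The point should be fixed. It concerns a safety rule, is partly mitigated by DSMB notice and patient-level stopping, and is cheap to close.

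**What to change.** Use one definition for both rules in Section 4.3.2:

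> *Trigger: if any of the six lead-in subjects has a definite BMX-001-related DLT as defined in Section 11.11, at any time until all six have completed the DLT period, accrual is suspended until the sponsor and DSMB have reviewed the event and a decision on the dose has been documented. Go condition: no such DLT.*

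Delete the parenthetical grade 3 description. Pointing to Section 11.11, rather than writing grade 3 or higher, also brings in the DLTs that carry no grade and keeps that section's exclusions, such as grade 3 alopecia.

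Two further steps:

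- The sponsor should confirm that *definite* is intended. Section 11.11 also counts possible and probable events, and 14.3 notifies on probable or definite ones.
- If the lead-in decision has already been taken, report which rule was applied and whether any definite grade 3 DLT occurred.

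The cost is a short rewrite in 4.3.2 and matching wording in the DSMB charter. The downside is a temporary pause after a single DLT that may prove transient, as the glioma hypotension did. No hold on enrolment is needed while the six complete their DLT periods.

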4.4 Rationale

4.4.1 Study Rationale

Patients undergoing CRT, typically with cisplatin-based regimens, can experience incapacitating acute and chronic functional disabilities in the form of dry mouth, loss of taste, mucositis or breakdown of the mucosal lining within the head and neck area, swallowing problems (dysphagia and odynophagia), and radiation dermatitis that can result in fibrosis and scarring of the skin and subcutaneous tissue. BMX-001 added to RT and cisplatin has the potential not only to benefit the survival of HN patients through improved tumor control but also to protect against the development of these types of toxicities and to prevent impairment of QoL. Therefore, we have started by performing a Phase 1 trial of BMX-001 at escalating doses in combination with standard RT, 30-35 daily fractions to 60-70 Gy, plus cisplatin at the standard of care dosing, which could be either dosing at 30-40 mg/m² administered IV once per week for 6-7 weeks or 100 mg/m² days 1 of RT and repeated q21 days for either 2 or 3 total doses. Cisplatin administration will be at the discretion of the treating team. Both regimens are considered acceptable standards within radiation oncologist-led cooperative groups such as the NRG. We hypothesize that BMX-001, when added to standard RT and cisplatin, will be safe at pharmacologically relevant doses in patients undergoing concurrent CRT for head and neck cancers. Since safety has been determined both in Dose Level 1 and Dose Level 2 for the Phase 1 portion of this study and for Dose Levels 1-3 in a separate Phase 1 safety study in patients with high-grade glioma, with establishment of an MTD, we will move to a Phase 2 expansion cohort to further study the safety and examine the effects of BMX-001 in combination with concurrent chemoradiation in the amelioration of mucositis, xerostomia, and radiation dermatitis in patients with stage III-IVb HNSCC.

4.4.2 Rationale for Selection of Dose, Regimen, and Treatment Duration

The recommended doses of BMX-001 are based on preclinical safety studies done in rats, mice, guinea pigs, dogs, and baboons, and the results of a completed Phase 1 trial in human subjects.

4.5 Quality of Life and Function Assessments

Before and during treatment for head and neck cancer, adult patients experience a decline in perceived HRQoL [30-35]. Liu defines HRQoL as "a concept that encompasses the multi-dimensional well-being of a person and reflects an individual's overall satisfaction with life." [31].

In order to capture fully the many aspects of HRQoL, we will utilize both objective and subjective measures to evaluate issues with fatigue and HRQoL. Subjectively, HRQoL is measured using patient-reported outcome questionnaires known as patient-reported outcomes (PROs). Four PROs will be used to assess functional status, self-reported measures of mucositis, self-reported measures of xerostomia, and self-reported measures of skin rash and discomfort: Functional Assessment of Cancer Therapy-Head & Neck (Version 4) (FACT-HN), Oral Mucositis Weekly Questinaire-Head+Neck (OMWQ-HN), Xerostomia-Related Quality of Life Scale (XeQoLS), and

Dermatology Life Quality Index (DLQI). The FACT-HN and first two questions of the OMWQ-HN measure overall HRQoL, which is the effect of disease and treatment on overall well-being. The remaining questionnaires are symptom or functional assessments. It has been shown that symptom and functional assessments provide necessary detailed information of the symptom burden on the patient that general measures of HRQoL are not sensitive enough to detect [36]. This data has also been shown to correlate poorly with toxicity scoring in some instances [37], making this information an important addition to the evaluation of treatment on well-being.

The FACT-HN version 4 is a multidimensional, self-report QoL instrument specifically designed for use with head and neck cancer patients (see Appendix B). It consists of 27 core items which assess patient function in four domains: Physical (Cronbach's $\alpha = .79$), Social/Family ($\alpha = .59$), Emotional (α = .59), and Functional Well-Being (α = .75), which is further supplemented by 12 site-specific items to assess for head and neck-related symptoms ($\alpha = .63$). The first four domains can be combined for a general assessment of function (FACT-G; α = .89) [38]. Each item is rated on a 0 to 4 Likert type scale and then combined to produce subscale scores for each domain, as well as a global QoL score. Higher scores represent better QoL [39]. The FACT-HN can be completed by the patient or by an interview and has an effect size of .55 [21]. The scale's sensitivity and ability to differentiate between known groups was tested by comparing the scale to Karnofsky performance status (low KPS < 80, high KPS > 80) and treatment status (on treatment vs. off treatment for greater than 3 months) and all domains were able to distiguish between good and poor performance at the p < .0001 level, except the emotional domain, p = .0001.08 [38]. The data also showed that 2-3 point differences on subscales appeared clinically meaningful. To determine convergent and discriminant validity, the FACT-HN was correlated with the Performance Status Scale for Head and Neck (PSS-HN), which includes 3 domains: normalcy of diet, understandability of speech, and eating in public [38]. As expected, the three scales of the PSS-HN were significantly correlated with the head and neck subsection of the FACT-HN (Spearman's r = 0.66, p < 0.0001; r = 0.17, p < .05; r = 0.42, p < 0.0001, respectively). Both diet and eating in public were also correlated with FACT-G (r = .24, p < .005; r = .20, p < .005.05). At least one construct from the PSS-HN was not correlated with each of the remaining constructs in the FACT-HN.

The OMWQ-HN is a 13 item functional assessment of mucositis using a Likert response format (See Appendix C). The items were developed by qualitative data provided by one on one interviews with 30 head and neck cancer patients [39]. Based on these results, questions were modified to ensure the scale was comprehensive, that there were no irrelevant questions, and for clarity of all items. The first two questions assess overall health and overall quality of life on a 7-point Likert scale. The third question quantifies overall mouth and throat soreness on a 5-point scale. The next six questions assess how much mouth and throat soreness limits certain activities on a 5-point scale. The last three questions further assess the degree of mouth and throat pain and soreness using an 11-point scale (overall Chronbach's α = .91). All items correlated strongly (Spearman's r's > .7) except the overall health and overall QoL items and the brushing teeth item (r < .5). Therefore these items are not calculated into the overall OMWQ-HN score.

To evaluate validity, the OMWQ-HN was given at four timepoints with the FACT-HN and PSS-HN to 75 patients with HNC who were receiving radiotherapy with or without chemotherapy [40]. The OMWQ-HN and the FACT-HN were significantly correlated ($\eta = -0.57$), however the OMWQ-HN and the PSS-HN were not as strongly correlated (η range = -0.09 to -0.37), suggesting that

syptoms from mucositis do not readily overlap with normalcy of diet, understandability of speech, and eating in public. Three levels of pain were assessed by a Likert scale which stated "I have pain" and had three response options: not at all/a little bit, somewhat, and quite a bit/very much. There was a significant difference in scores on the OMWQ-HN depending on this variable, F(2.62) = 38.6, p < .001, ES = .77-.99. There was also significant divergence between patients who used opioid analgesics compared to those who did not, such that those who were using analgesics scored worse (p = .002, ES = 0.87). Timepoints were 24-48 hours apart, providing a test-retest correlation of .89. Sensitivity to change was shown by determining changes in the pain item and normalcy of diet item to compare OMWQ-HN scores between no change/improved groups and worsened groups, t(63) = -4.3, p < .001, and t(63) = -2.6, p = .013, respectively. It has also been shown that the OMWQ-HN is more responsive than less symptom-focused QoL instruments in detecting early changes in symptoms related to oral mucositis [40].

The subjective impact of salivary gland dysfunction and xerostomia is assessed by collecting stimulated and unstimulated saliva production (See Section 13.1.6) and by using the Xerostomia-Related Quality of Life Scale (XeQoLS) developed at the University of Michigan (Appendix D). In its first form, the XeQoLS contained 8 questions developed through literature reviews, patient surveys, and the input of oncologists specializing in head and neck cancer, and was shown to parallel clinically measured salivary gland function [40-42]. Research showing that there were four domains to oral health-related quality of life led to the current 15 item scale that covers physical functioning (Cronbach's α = .85), personal/psychological functioning (α = .87), social functioning (α = .86), and pain/discomfort issues (α = .89). The Cronbach alpha coefficient for the total XeQoLS score was also significant (α = .96, p < 0.001) [43]. Internal validity was assessed by comparing the 15 item xeQoLS to the previous 8 item version (α = .36 to .73, p < 0.001). Correlations were significant between the scale and salivary flow (r =-.19 to -.28, p < .05) and there were expected between group differences when comparing those who had parotid-sparing radiotherapy compared to those that did not such that parotid-sparing provides better XeQoL [43].

The Dermatology Quality of Life Index (DLQI) is a well established 10 item questionnaire used to assess impacts of skin irritation on patients well-being and functionality (Appendix E). Although the DLQI was first developed to treat disorders of the skin, it has been validated in over 30 different skin dysfunctions and has been shown to be a valid measure for erythema, inflammation, atopic eczema, and pruritus. It is currently being used to assess radiation-induced damage in two large head and neck cancer studies, including RTOG 0920 [44,45]. The DLQI consists of 10 items and covers 6 domains including symptoms and feelings, daily activities, leisure, work and school, personal relationships, and treatment. Scores are on a 4-point Likert scale from "not at all," to "very much," and each has an option of "not relevant," with higher scores indicating worse HRQoL. Score differences of 4 points have been shown to be statistically significant [46-50]. The scale was shown to distinguish between pre-emptive treatment vs. reactive treatment to radiation-induced skin toxicities in a colorectal cancer patient population [51].

5 Objectives

5.1 Phase 1

